4 STUDY DESIGN

4.1 OVERALL DESIGN

This study will examine the effectiveness of MI assistance on the medication verification process in a mock setting. Pharmacists with medication dispensing experience will be recruited to perform mock verification tasks on a web application on the computer. Webcam-based eye-tracking software will be used to detect eye gaze patterns during verification tasks (<https://www.labvanced.com/>).

Participants will attend one 3-hour remote visit. During this visit, participants will complete a series of 300 remote verification tasks. Prior to starting the verification tasks, participants will complete 3 surveys: 1) a demographics survey 2) the propensity to trust scale²⁰ and 3) the Occupational Fatigue Exhaustion Recovery Scale.²¹ Each participant will then receive a 15-minute self-guided training session that introduces the study and teaches participants how to use the interface and perform the medication verification task. In each verification task, participants will compare the image on the left (i.e., the medication filled for a prescription) to the image on the right (i.e., a known reference image) and decide whether to accept or reject the images as containing the same prescribed medication.

Pharmacists will be presented with 3 conditions: No help group, Scenario #1, and Scenario #2 (see Figure 1). The order of the conditions will be randomized. In the No help group, participants will complete the verification task without any artificial intelligence (AI) help. In Scenario #1, participants will receive AI in the form of a pop-up message if their decision differs from the AI's determination. In Scenario #2, AI help will be displayed concurrently with the filled and reference images.

After each verification task in Scenario #1 and Scenario #2, the participants will be asked to respond to a visual analog trust scale (e.g., How much do you trust the automation with the left anchor "I completely distrust the MI" and the right anchor "I completely trust the MI"?).^{20,22} After each condition, participants will complete 2 brief surveys - System Usability Scale,²³ NASA Task Load Index.²⁴ After Scenario #1 and Scenario #2, participants will also complete a trust scale.²⁵

To approximate a real-world experience in this mock setting, 20% of images provided in these verification tasks for each participant will differ from labels in prescriptions (i.e., an incorrectly filled prescription).

Figure 1. Interfaces for each study condition evaluating the effect of machine intelligence (MI) on work performance and pharmacist trust. Top: No MI help; Middle: MI help; Bottom: AI help when disagreement between user and AI

5 STUDY POPULATION

5.1 INCLUSION CRITERIA

To be eligible to participate in this study, an individual must meet all the following criteria:

1. Licensed pharmacist in the United States
2. Age 18 years and older at screening
3. PC/Laptop with Microsoft Windows 10 or Mac (Macbook, iMac) with MacOS with Google Chrome, Edge, Opera, Safari, or Firefox web browser installed on the device

4. Screen resolution of 1024x968 pixels or more
5. A laptop integrated webcam or USB webcam is also required for the eye tracking purpose.

5.2 EXCLUSION CRITERIA

1. Participated in Wave 1 or Wave 2
2. Eyeglasses
3. Uncorrected cataracts, intraocular implants, glaucoma, or permanently dilated pupil
4. Require a screen reader/magnifier or other assistive technology to use the computer
5. Eye movement or alignment abnormalities (lazy eye, strabismus, nystagmus)

5.3 STRATEGIES FOR RECRUITMENT AND RETENTION

Pharmacists will be recruited from 3 recruitment pools of pharmacists who have expressed interest in this study or in research in general. They include the Minnesota Pharmacy Practice-Based Research Network, PearlRx (a University of Wisconsin-Madison based pharmacy practice-based research network), and the University of Michigan College of Pharmacy Pharmacist Preceptor Network. These 3 recruitment pools have more than 3000 registered pharmacists who may be eligible to participate in the study.

Email communication will be delivered to advertise the study and help ensure adequate participation in the study to reach recruitment goals. Participants will receive \$100 for completing the study visit.

Participation is limited to one remote study visit. As such, we do not anticipate any need for a formal retention plan.

6 STUDY INTERVENTION

6.1 MEASURES TO MINIMIZE BIAS: RANDOMIZATION AND BLINDING

The order of conditions will be randomization will occur using Labvanced's customizable randomization scheme. This will be a stratified random sample with balanced assignment to each study condition.

This is an unblinded study. Participants and researchers will know the randomization group.

7 STATISTICAL CONSIDERATIONS

7.1 STATISTICAL HYPOTHESES

- Primary Endpoint(s):

We hypothesize reaction time and accuracy will be different between the three scenarios.

We hypothesize trust will be a difference between scenario 1 and scenario 2.

- Secondary Endpoint(s):

We hypothesize there will be a difference in cognitive effort, workload, and usability between the three scenarios.

7.2 SAMPLE SIZE DETERMINATION

For the within-subject design to obtain 95% power with a 95% confidence interval, 36 subjects are required to detect a statistically significant difference in detection rates between the experimental groups.

7.3 STATISTICAL ANALYSES

7.3.1 ANALYSIS OF THE PRIMARY AND SECONDARY ENDPOINT(S)

ANOVA and/or mixed linear and mixed generalized linear models will be used to test the difference in task time, trust, detection rate, and cognitive effort among the three study conditions. The family-wise error rate will be set at a value of no greater than 0.05 to account for the 3 pairwise comparisons. ANOVA and Fisher's exact test are used when comparing independent proportions. All statistics will be performed using R (version 3.6.1). The ANOVA test and Fisher's exact test will be computed with the stats library.

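### Section 7.3.1 names no period effect for a three-block crossover visit. Common drift would not bias the condition contrasts, but without a period term it inflates the reported standard error and lowers power.

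*Combined protocol and SAP*

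**What the plan says.** Section 4.1 describes one 3-hour remote visit in which "participants will complete a series of 300 remote verification tasks" under three conditions. Questionnaires follow each condition, which implies three successive blocks. On sequence it says "The order of the conditions will be randomized". Before the tasks, "Each participant will then receive a 15-minute self-guided training session".

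Section 6.1 opens with a garbled sentence about order ("The order of conditions will be randomization will occur using" the platform's randomisation scheme) and continues: "This will be a stratified random sample with balanced assignment to each study condition". It names neither the six orders nor any strata.

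On method, Section 7.3.1 says that "ANOVA and/or mixed linear and mixed generalized linear models will be used". Their purpose, for primary and secondary endpoints alike, is given as to "test the difference in task time, trust, detection rate, and cognitive effort among the three study conditions". No period, order or random-effect term is listed, and none is ruled out. Fisher's exact test is also named, for independent proportions. Section 7.2 gives 36 participants for 95% power on detection rates and states no effect size, SD or test.

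**The concern.** Over 300 tasks on a newly taught interface, participants may speed up, tire, or both. A participant who meets a condition in block 1 is then measured under different circumstances from one who meets it in block 3. If the model contains condition and participant but not block, this predictable variation is counted as noise.

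The stake is the power of a 36-participant study for its primary endpoints. If the orders are not used equally, chance imbalance in block position between conditions is added. The block number is known for every task, so the remedy needs no extra data.

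**Working it through.** **Inputs.** From the documents: n=36 and 95% power (7.2); three conditions per participant, 300 tasks and 20% mismatches (4.1). Assumed: two-sided 0.05 per comparison with no multiplicity adjustment; 95% power holds in the absence of drift; drift is linear and common to all participants, d per block in SDs of the paired difference. The documents give no drift value.

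**The plan's own figure.** N=36 cannot be reproduced, because 7.2 gives no inputs. Back-solving a paired t-test, P(T₃₅(δ·√36) > 2.030) = 0.95 gives δ = 0.618, so the noncentrality is 0.618 × 6 = 3.708.

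**How drift enters.** Over the six orders, two given conditions are one block apart in four orders and two blocks apart in two, with signs that cancel. The mean position difference is 0 (no bias) and its mean square is (4×1 + 2×4)/6 = 2. Drift therefore adds 2d² to the variance of the paired difference between participants.

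**Three-condition model without period.** Residual df = 108 − 36 − 2 = 70, and the critical t is 1.994.

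- Equal orders: drift cancels from the condition means, so the true SE stays at 1/6 = 0.167. Each participant adds 2d² to the residual sum of squares, 72d² in all, so the reported SE is inflated by k = √(1 + 2×72d²/70). Power = P(T₇₀(3.708) > 1.994k).
- Independent random orders: the estimate itself varies more. Power = P(T₇₀(3.708/√(1+2d²)) > 1.994).

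| d per block | k | Equal orders: power | Equal orders: type I error | Random orders: power |
|---|---|---|---|---|
| 0 | 1.00 | 95.5% | 5.0% | 95.5% |
| 0.1 | 1.01 | 95.3% | 4.8% | 95.2% |
| 0.25 | 1.06 | 94.2% | 3.8% | 93.2% |
| 0.5 | 1.23 | 89.2% | 1.7% | 84.8% |
| 0.75 | 1.47 | 77.8% | 0.5% | 70.9% |

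Simulation agrees to within a point. With period in the model, simulated power is about 95% at every drift, under equal or random orders.

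**Detection-rate scale.** Since "20% of images provided in these verification tasks for each participant will differ from labels in prescriptions", there are 0.20 × 300 = 60 mismatches, or 20 per condition if split evenly (assumed). At an assumed 85% detection rate, the SD of the paired difference is √(2×0.85×0.15/20) = 11.3 points. So d=0.5 is about 5.6 points per block and d=0.75 about 8.5 (17 points from first to third block). At 70% and 95% detection, d=0.5 is 7.2 and 3.4 points. Simulated participant-level power at 85% detection, with drift of 1, 3 and 5 points per block, is 95.0%, 93.6% and 90.3% with equal orders, and 94.9%, 92.4% and 86.9% with random orders.

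**Trial-level analyses with random orders.** If single trials are the error unit, the contrast variance is understated by a factor of about 1+2d². Type I error is then about 2Φ(−1.96/√(1+2d²)) = 6.5%, 11.0% and 17.9% at d = 0.25, 0.5 and 0.75; simulation of a participant-intercept-only model gave 6.3%, 11.0% and 17.6%. Fisher's exact test on pooled trials, with 5.6 points of drift per block at 85% detection, rejected in about 8 to 9% of null runs. With equal orders, the intercept-only model stayed near 5% and Fisher's test was at about 4%.

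**The case against.** The strongest reply is that the plan already has the main safeguard. Order is randomised, and since every participant receives every condition, balance in 6.1 has content only if it refers to order. On that reading the random-order results fall away. What remains is a conservative test, not an invalid one. This stands, and it is why the point is minor.

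A reader might go further and infer that leaving out period biases the condition effects, that true precision is lost, or that the plan inflates type I error. The documents support none of these. Randomised order removes bias on average. With equal orders only the reported standard error suffers. The inflated rejection rates need unequal orders together with an analysis that treats trials as independent, a combination the wording allows but does not specify.

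Two further objections hold in part. The larger drifts are large for detection rate, the endpoint on which 7.2 bases its sample size, and the training session may reduce learning effects. Also, the 95% baseline is taken as drift-free. If the undisclosed planning SD already contained order variation, the period term would add power above plan instead of restoring it. Neither is a reason to leave the term out.

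**Conclusion.** The concern holds as a minor one. With equal orders and no period term, the condition estimates are sound but their standard errors are overstated. Power falls from about 95% to about 94%, 89% and 78% at assumed drift of 0.25, 0.5 and 0.75 SD per block, and by less than 1 point at 0.1 SD. For detection rate at 1 to 3 points per block, the loss is about 0 to 1.4 points.

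If orders are not equal, there is real chance imbalance as well (about 93%, 85% and 71% power), and trial-level analyses can exceed 5% type I error.

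The sizes rest on assumed drift, a drift-free 95% baseline and unadjusted 0.05 tests. At 0.0167 per comparison the pattern is the same: with drift of 0.25, 0.5 and 1.0 within-condition SDs per block (about 0.18, 0.35 and 0.71 SD of the paired difference), power without period is 95%, 93% and 76% with equal orders, against 94 to 96% with period. The absence of bias is exact for linear models. In a logistic model, omitting period pulls the odds ratio slightly toward 1 (under 2.5% on the log scale at 0.5 logit per block, for assumed baseline accuracy of 80 to 95%).

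**What to change.** In 7.3.1, prespecify period (block 1, 2, 3) as a fixed effect, with participant as a random effect, in every model that compares conditions. In 6.1, state: 'Participants will be randomised in balanced blocks to the six possible orders of the three conditions (6 per order at n=36).'

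The cost is one line and one sentence. Period uses 2 of 70 within-participant error degrees of freedom for three-condition outcomes, and 2 of 35 for trust, which has two conditions (72 − 36 − 1 = 35). With no drift, power changes by about 1 point or less.

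One limit should be understood: the term removes drift common to participants. It does not recover power lost when drift differs between them. With a between-participant drift SD of 0.5 or 0.75 per block and equal orders, power is about 85% or 71% with or without period.

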Furthermore, little is known about the timing of the MI advice on pharmacists' work performance. For example, showing the MI's advice while the pharmacist is performing the medication verification task may yield different results than showing the MI's advice after the pharmacist made their decision.

The study investigators have developed a MI system for medication images classification. The objective of this study is to examine the effectiveness of the timing of MI advice to determine if it results in lower task time, increased accuracy, and increased trust in the MI. The objectives of this study are to: 1) evaluate changes in participants' trust due to the use of interpretable machine intelligence; and 2) determine the effect of interpretable machine intelligence on participants' performance in a simulated environment.

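### Does leaving the multiplicity procedure unnamed in section 7.3.1 put the 0.05 family-wise cap, or the pairwise conclusions, at risk?

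*Combined protocol and SAP*

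**What the plan says.** Section 7.3.1 fixes a level and a count: "The family-wise error rate will be set at a value of no greater than 0.05 to account for the 3 pairwise comparisons". It does not say which adjustment delivers that level, or whether the overall test must be significant before pairs are examined. The model is open as well: "ANOVA and/or mixed linear and mixed generalized linear models will be used to test the difference in task time, trust, detection rate". The same sentence also covers the eye-tracking measures of effort.

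The hypotheses in section 7.1 are stated across conditions for time and accuracy: "We hypothesize reaction time and accuracy will be different between the three scenarios". For trust, section 7.1 names only Scenario #1 against Scenario #2, so trust has a single comparison and needs no adjustment over three pairs.

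Section 7.2 gives the sample size: "For the within-subject design to obtain 95% power with a 95% confidence interval, 36 subjects are required to detect a statistically significant difference". The endpoint it refers to is the detection rate. It states no effect size, detection rates, standard deviation, within-person correlation or per-comparison alpha. It also does not say whether the 95% refers to the overall test or to a pair.

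**The concern.** A cap without a procedure lets two analysts obey the same sentence and report different pairs as significant from the same 36 pharmacists. The stated interest makes this look important. Section 2.1 says "The objective of this study is to examine the effectiveness of the timing of MI advice", which is the contrast of Scenario #1 with Scenario #2, and a significant overall test does not answer that question by itself. The contrasts most exposed to the choice are those smaller than the largest one, and the timing contrast could be one of them.

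Two further worries follow. If the procedure were picked after results were known, the cap would no longer strictly hold, and section 6.1 says "This is an unblinded study. Participants and researchers will know the randomization group". And a non-significant pair might be read as the result of a 95%-powered test, although section 7.2 does not show that power for any single pair.

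**Working it through.** **Inputs from the documents.** Three conditions seen by every participant (section 4.1), so 3 pairs; 36 participants and 95% power (section 7.2); family-wise cap 0.05 (section 7.3.1). The 95% confidence interval in section 7.2 is read as two-sided alpha 0.05. Error degrees of freedom for a repeated-measures ANOVA: (36 − 1) × (3 − 1) = 70.

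**The 36 cannot be reproduced**, because no effect size is given. The effect it implies can be back-solved at 95% power:
- one pair, paired t, two-sided 0.05: standardised paired difference 0.618;
- one pair at 0.05/3: 0.702;
- overall F(2, 70) at 0.05: noncentrality 16.13. With the SD of a paired difference set to 1, noncentrality is 72 × (sum of squared deviations of the three means). For means (0, 0, d) this is 48d², so d = √(16.13/48) = 0.580. For (0, d/2, d) it is 36d², so d = √(16.13/36) = 0.669.

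**Does each procedure hold the cap?**
- Bonferroni: 3 × 0.05/3 = 0.05. Holm steps through 0.05/3, 0.05/2 and 0.05, with the same guarantee.
- Tukey is built for all pairs at 0.05.
- Gated unadjusted tests: if all means are equal, the overall test limits error to 0.05. If two are equal and one differs, only one pair is truly null and it is tested at 0.05. If all differ, no false rejection is possible.

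So all four comply when chosen in advance.

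**Why they differ.** On 70 df a pair needs |t| above 2.453 (Bonferroni, two-sided 0.05/3), 2.395 (Tukey), 2.453 then 2.291 then 1.994 (Holm's three steps), or 1.994 once the overall F passes (gated). Disagreement arises only for pairs falling between about 1.99 and 2.45.

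**How often they differ.** Simulated trials of 36, 60,000 per case, normal outcomes, equal correlation, complete data, one pooled error term. Share with any disagreement among the four procedures on any of the three pairs:

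| How 36 was sized | One condition differs | Means evenly spaced, end-to-end gap fixed |
|---|---|---|
| Overall F-test | 15.6% | 32.0% |
| One pair at 0.05 | 12.9% | 31.2% |
| One pair at 0.05/3 | 7.7% | 32.1% |

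The upper end comes from setting Bonferroni against gated tests (31.7% in the evenly spaced case under overall-F sizing). With Bonferroni, Holm and Tukey alone the six cells run from about 5 to 20%; Bonferroni against Tukey gives 1 to 5%. Separate paired t-tests instead of a pooled error move the range to 10 to 37%, and mixing separate and pooled error terms takes it to about 40%.

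A binomial version used section 4.1's "20% of images provided in these verification tasks for each participant will differ from labels in prescriptions": 0.20 × 300 = 60 mismatches, 60/3 = 20 per condition if split evenly (an assumption). Under overall-F sizing it gave 16 to 20% (one condition differs) and 32 to 33% (evenly spaced).

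**The range depends on the assumed pattern.** Means (0, d, 2d) sized for a pair at 0.05/3 give about 5 to 6%; no true difference gives about 2.6%.

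**By contrast.** Disagreement on the largest contrast alone is 1 to 7% over the six cells. It is 16 to 17% for a contrast half that size.

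**Cost of choosing afterwards.** With no true difference, the chance that at least one of the four procedures rejects at least one pair is 5.5% with pooled error and 6.1% with separate paired t-tests (simulation error about 0.1 percentage point). That is 0.5 to 1.1 percentage points above the cap, for an analyst who always reports the most favourable answer.

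**Power.** If 36 was not sized at an adjusted alpha, the largest or sized-for pair has about 83% to just under 95% power after adjustment, and half-size contrasts about 27 to 49%. If 36 was sized at the adjusted alpha, or if the 95% is the power of the overall test, the stated 95% loses nothing.

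**The case for a change.** The best case for a change is that the omission is real, nothing else in the documents fills it, and the remedy is a sentence that costs no participants. Pairwise conclusions carry the timing question, and disagreement in as many as a third of trials under a plausible pattern is not trivial. Leaving the model open widens the spread further.

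The omission stands, and so does the fact that some pairwise calls will turn on the choice. The rest weakens on inspection.
- The disagreement rates depend on patterns of means and effect sizes that the documents do not contain, so they are illustrations and not properties of this plan. Nor do the documents say that Scenario #1 against Scenario #2 is a half-size contrast.
- The measure is severe: it counts any mismatch among four procedures on any of three pairs. Its upper end needs unadjusted gated tests, which are valid with three conditions but are a less natural reading of a sentence about accounting for the pairwise comparisons.
- The unblinded design bears little on this. Every participant meets all three conditions, and knowing the condition says nothing about when the adjustment is chosen. Nothing in the documents suggests it would be chosen after results are seen.
- Section 7.2 speaks of detecting a difference between the experimental groups. It makes no 95% claim for each pair, so the power worry concerns a possible misreading and not something the plan asserts.

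**Conclusion.** No change to the plan follows. This is missing detail that a competent analyst fills within the rule already given: the plan sets the error level and the number of comparisons, and any of the standard procedures for three conditions honours both. No stated rule or figure is shown to be wrong, and no inferior method is prescribed that a better one should replace.

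The disagreement between procedures is mostly a matter of which real but moderate differences get declared, not of false claims, and the effect on error control is about one percentage point at worst. That is small for a study that section 1.1 describes as a formative evaluation in a simulated setting.

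The conclusion that each procedure holds the cap does not depend on the assumed pattern of means. Tukey and the pooled-error tests do assume similar variances for the three paired differences. The disagreement percentages rest on the back-solved effects being true, on the two main patterns of means, and on normal or simple binomial data without missing values.
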